5.6 Urine Pregnancy Test

[REDACTED]

5.7 Dermatological Assessment (Diagnosis)

The investigator or sub-investigator will examine the subject to establish the clinical diagnosis of Actinic Keratosis defined as the presence of 4 to 8 clinically typical, visible, discrete, nonhyperkeratotic, nonhypertrophic Actinic Keratosis lesions, contained within a contiguous 25cm² area on the head region (face or scalp), excluding the nose. Subjects should be enrolled in the study only if a 25cm² contiguous area is identified as the treatment area containing 4 to 8 clinically, visible discrete Actinic Keratosis lesions on the face or scalp, excluding the nose.

5.8 Fitzpatrick Classification Scale

The Fitzpatrick skin scale classifies a person's complexion and their tolerance of sunlight. It is commonly used by many practitioners to determine how someone will respond or react to facial treatments, and how likely they are to get skin cancer.

At Visit/Day 1 (Baseline), the Principal Investigator (PI) or Sub-Investigator (Sub-I) will examine the subject's skin to determine the skin type by using the Fitzpatrick scale below and will indicate the skin type on the source document and eCRF.

Skin Type	Skin Color	Characteristics
I	White; very fair; red or blond hair; blue eyes; freckles	Always burns, never tans
II	White; fair; red or blond hair; blue, hazel, or	Usually burns, tans with difficulty

[REDACTED]

	green eyes	
III	Cream white; fair with any eye or hair color; very common	Sometimes mild burn, gradually tans
IV	Brown; typical Mediterranean Caucasian skin	Rarely burns, tans with ease
V	Dark Brown; mid-eastern skin types	very rarely burns, tans very easily
VI	Black	Never burns, tans very easily

5.9 Clinical Actinic Keratosis Lesion Counting & Assessment

Each subject's initial condition and course of Actinic Keratosis will be assessed by counting the number of lesions located within the designated treatment area on the face or scalp (excluding the nose). At Visit 1/Day 1 (Baseline), the PI or study staff should select an area of 25cm² [REDACTED] to be treated with the study medication gel as the designated treatment area on the face or scalp (excluding the nose). This selected treatment area should have 4 to 8 visible clinically, discrete Actinic Keratosis lesions within a 25cm² contiguous treatment area. Additionally, The PI or designated staff will document the location of each lesion, the designated treatment area and the size (in cm²) of the treatment area at Visit 1/Day 1 (Baseline) as part of the subject's source documentation. The location of the designated treatment area will be recorded on the facial (i.e., upper right quadrant, lower right quadrant, upper left quadrant or lower left quadrant) or scalp anatomical diagram [REDACTED] in the subject's source documentation. In the event that the designated treatment area falls into more than one quadrant, the PI or designated staff will specify the two quadrants on the facial or scalp diagrams. Plastic transparencies will also be provided to map the designated treatment area and location of each AK lesion at Visit 1/Day 1 (Baseline) and serve as a location guide for assessment of the application site reaction at subsequent visits, Actinic Keratosis lesion count, and identification of (old and new) Actinic Keratosis lesions at Visit 4/Day 57, and Unscheduled Visit, if applicable. A transparency (or transparencies) will be made for the subject to assist with locating the designated treatment area. Study staff should mark important and permanent landmarks on the transparencies (i.e., a furrow, mole, tip of ear, nose, eyebrows, etc.) and each lesion with an X within the designated treatment area.

Subjects with hypertrophic and hyperkeratotic lesions in the treatment area will be excluded from the study.

To the extent possible, the same investigator who made Visit 1/Day 1(Baseline) assessments will perform evaluations at Visit 4/Day 57. At Visit 1/Day 1(Baseline), Visit 4/ Day 57, and Unscheduled Visit, if applicable, the number of Actinic Keratosis lesions within the treatment

area will be counted and recorded in the source documentation and eCRFs. Additionally, at Visit 4/Day 57, and Unscheduled Visit, if applicable, , new Actinic Keratosis lesions as compared to Visit 1/Day 1 (Baseline) will be counted and recorded in the source documentation and eCRFs. Additionally, the PI or designated staff will give to each subject copies of photographs of expected application site reactions (erythema, flaking/scaling, crusting, swelling, vesiculation/postulation, and erosion/ulceration) for examples of what may be expected.

Complete clearance (Actinic Keratosis lesion count in the selected treatment area) at Visit 4/Day 57 will be assessed. Complete clearance is defined as no (zero) clinically visible Actinic Keratosis lesions (including presence of new lesions) in the selected treatment area at Visit 4/Day 57. The investigator or sub-investigator will confirm the number of lesions in the selected treatment area (including new lesions) and clinical response success if lesion count is equal to zero at Visit 4/Day 57.

[REDACTED]

Lesion counting must be conducted by qualified investigators or designated staff listed on the Form FDA 1572 who have been delegated these tasks by the PI. [REDACTED]

[REDACTED]

5.10 Application Site Reaction Assessment

To the greatest extent possible, the same investigator who made Day 1 (Baseline) assessments will assess the application site reactions, grade them according to a 5-point scale and a designated staff will record them in the source document and eCRFs at each subsequent visit. This assessment must be conducted by qualified individuals listed on the Form FDA 1572 who have been delegated this task by the PI. [REDACTED]

[REDACTED]

At baseline (prior to initial dosing) and each subsequent visit, application site reactions of erythema, flaking/scaling, crusting, swelling, vesiculation/pustulation, and erosion/ulceration are to be recorded in the source document and eCRFs.

Application site reactions (erythema, flaking/scaling, crusting, swelling, vesiculation/pustulation, and erosion/ulceration) are not to be recorded as adverse events unless they result in either:

- The temporary discontinuation of the study medication.
- The discontinuation of the subject from the study.

[REDACTED]

Protocol No: PRG-NY-14-019

- The use of a new concomitant medication in order to treat this event.

Any other application site reaction not listed above (such as pain, pruritus and infection) should be recorded as adverse events in the source document and eCRFs.

The following scale will be used for the Application Site Reaction Assessment:

Site Reaction	DESCRIPTION
Erythema	[REDACTED]
Flaking/scaling	[REDACTED]
Crusting	[REDACTED]
Swelling	[REDACTED]
Erosion/ulceration	[REDACTED]
Vesiculation/pustulation	[REDACTED]

Site Reaction	Grading Criteria				
	0 (clear)	1 (almost clear)	2 (mild)	3 (moderate)	4 (severe)
Erythema	Not present	[REDACTED]	[REDACTED]	[REDACTED]	[REDACTED]
Flaking/scaling	Not present	[REDACTED]	[REDACTED]	[REDACTED]	[REDACTED]
Crusting	Not present	[REDACTED]	[REDACTED]	[REDACTED]	[REDACTED]
Swelling	Not present	[REDACTED]	[REDACTED]	[REDACTED]	[REDACTED]
Erosion/ Ulceration	Not present	[REDACTED]	[REDACTED]	[REDACTED]	[REDACTED]
Vesiculation/ pustulation	Not present	[REDACTED]	[REDACTED]	[REDACTED]	[REDACTED]

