Study Visits:	
Clinical Evaluations will be performed at:
 
 1. Visit 1/Day 1 (Baseline) 2. Visit 2/Day 4 (+1 day) (Post-Treatment Interim) 3. Visit 3/Day 29 (±3 days) (Interim) 4. Visit 4/Day 57 (±2 days) (End of Study) 
Safety will be assessed by monitoring adverse events at each visit and

	during a Follow-Up Phone Call/Day 15 (± 3 days).
Evaluations:	
The investigator or sub-investigator will examine the subject to establish the clinical diagnosis of Actinic Keratosis defined as the presence of 4 to 8 clinically typical, visible, discrete, nonhyperkeratotic, nonhypertrophic Actinic Keratosis lesions, contained within a contiguous 25cm² area on the head region (face or scalp) excluding the nose. At the baseline visit, a treatment area of 25cm² contiguous area located in the face or scalp excluding the nose will be identified by the investigator or sub-investigator and selected as the treatment area.
 
The number of Actinic Keratosis lesions in the selected treatment area will be counted (and a total provided) at Visit 1/ Day 1(Baseline), Visit 4/Day 57 and Unscheduled Visit (if applicable), will be recorded on source documentation and eCRFs. Additionally, new lesions not present at the Baseline visit will also be counted and recorded on source documentation and eCRFs at Visit 4, and Unscheduled Visit, if applicable.
 
Complete clearance (Actinic Keratosis lesion count in the selected treatment area) at Visit 4/Day 57 will be assessed. Complete clearance is defined as no (zero) clinically visible Actinic Keratosis lesions (including presence of new lesions) in the selected treatment area at Visit 4/Day 57. The investigator or sub-investigator will confirm the number of lesions in the selected treatment area and clinical response success if lesion count is equal to zero at Visit 4/Day 57.
 
At baseline (prior to initial dosing) and each subsequent visit, application site reactions of erythema, flaking/scaling, crusting, swelling, vesiculation/pustulation, and erosion/ulceration will be recorded on the source document and eCRF.

Endpoints:	The primary efficacy endpoint will be the proportion of subjects with clinical success defined as complete clearance (absence) of all clinically visible Actinic Keratosis lesions identified at the baseline visit and no new Actinic Keratosis lesions in the treatment area at Visit 4/Day 57.

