3 STUDY DESIGN

3.1 Type/Design of Study

Subjects in this multi-center, double-blind, randomized, vehicle-controlled, parallel-group study will be assigned [REDACTED] to test product, reference product, or vehicle, respectively. The study medication will be dispensed at Visit 1/Day 1 (Baseline) to subjects meeting all entry criteria. The assigned study medication will be applied topically [REDACTED] to the designated treatment area (up to one contiguous skin area of approximately 25cm² on the head region (face or scalp) once daily for three (3) consecutive days, avoiding contact with the eyes, mouth and other body areas during and after gel application.

Subjects will be healthy males and females, at least 18 years of age, with 4 to 8 clinically typical, visible and discrete, nonhyperkeratotic, nonhypertrophic Actinic Keratosis lesions within a contiguous 25cm² treatment area on the head region (face or scalp) excluding the nose. Visits to the study site are scheduled at Day 1 and Day 4, Day 29, and Day 57. There will also be a phone call at Day 15 to follow up on previously reported adverse events by the subjects.

At Visit 1/Day 1/Baseline written informed consent will be obtained. The subject's demographic profile, medical history, and prior/concomitant medication use will be recorded. A urine pregnancy test will be performed for all women of childbearing potential. A brief physical examination (including heart, lung and abdomen evaluations) including vital signs and height/weight will be recorded during baseline.

The subject's history of Actinic Keratosis will be evaluated at Visit 1/Day 1 (Baseline). A dermatological exam and Actinic Keratosis lesion assessment will be conducted at Visit 1/ Day 1(Baseline), and Visit 4/Day 57, and if necessary at an Unscheduled visit. Subjects who meet all of the inclusion and none of the exclusion criteria will be enrolled in the study, [REDACTED]

[REDACTED] and given a daily diary to complete. Instructions on proper treatment application and completion of the diaries will be provided to subjects and the rest of their visits will be scheduled. During the baseline visit, the study staff will demonstrate proper medication application to the subject and then observe the subject applying their initial application to ensure subjects understand the instructions. The study staff should instruct the subject to [REDACTED]

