apply all subsequent doses of the study medication at approximately the same time of day on Days 2 and 3 (starting on Day 2 of study treatment period).

Subjects will return to the study site at Visit 2/Day 4 (Post-Treatment). During this visit, the completed subject diary will be collected, a new diary will be given to the subject and the Principal Investigator or designated staff will perform a dermatological exam of the treatment area and determine the application site reaction symptom scores. Subjects will return all study medication, and study medication accountability will be done. Information on concomitant medication use and protocol compliance will be collected and reviewed. Safety will be assessed by the monitoring of the subject's adverse events (AEs). At this visit, the Follow-up Phone call/Day15, Visit 3/Day 29 and Visit 4/Day 57 will be scheduled.

A Follow-up telephone call will be made at Day 15 to each subject to review and assess subject compliance, record AEs, update concomitant medication use, and to remind the subjects of the protocol requirements and next study visit schedule.

At each subsequent study visit, Visit 3/Day 29 and Visit 4/Day 57 (End of study), concomitant medications and protocol compliance will be discussed with the subject. The completed subject diary will be collected, reviewed with the subject and a new diary will be dispensed at Visit 3/Day 29. The completed subject diary dispensed at Visit 3/Day 29 will be reviewed and collected at the subsequent visit (Visit 4/Day 57). Safety will be assessed by the monitoring of all adverse events (AEs) and clinically significant changes from Visit 1/Day 1 (Baseline) and an application site reaction assessment will be conducted at Visit 3/Day 29 and Visit 4/Day 57.

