7. ADVERSE REACTIONS

The potential adverse reactions of generic Ingenol Mebubate Topical Gel 0.015% are anticipated to be similar to those observed in Picato[®] Topical Gel (Ingenol Mebutate Topical Gel 0.015%). The most common adverse reactions related to treatment with Picato[®] Topical Gel include local skin reactions, application site pain, application site pruritus, application site irritation, application site infection, periorbital edema, nasopharyngitis and headache. Eye disorders, including severe eye pain, eyelid edema, eyelid ptosis, periorbital edema can occur after exposure. Severe local skin reactions such as vesiculation/postulation, erosion/ulceration can occur.

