The severity of application site reactions such as erythema, flaking/scaling, crusting, swelling, vesiculation/pustulation, and erosion/ulceration will be summarized by treatment group and visit using frequencies and percentages of subjects.

[REDACTED]

6 Appendices

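### On the visible text, an untreated site reaction that arises or worsens after Visit 2 and heals before Visit 3 has no required place in the data, even if the subject reports it

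*Protocol*

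**What the plan says.** Protocol 5.10 sets the grading rule on a 0-to-4 scale: "At baseline (prior to initial dosing) and each subsequent visit, application site reactions of erythema" and five other reactions are scored. Section 3.1 fixes the visits: "Visits to the study site are scheduled at Day 1 and Day 4, Day 29, and Day 57". The synopsis gives the windows as Day 4 (+1), Day 29 (±3) and Day 57 (±2). At Visit 2 the investigator or designee is to "determine the application site reaction symptom scores", and 3.1 requires the assessment again at Visits 3 and 4.

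Section 5.10 also limits when the six reactions enter the adverse event record. They "are not to be recorded as adverse events unless they result in either" a temporary stop of study medication, the subject's discontinuation from the study, or a new medication to treat the reaction. Site reactions outside the six, such as pain, itching or infection, are recorded as adverse events.

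The only scheduled contact between Visits 2 and 3 is by telephone: "A Follow-up telephone call will be made at Day 15 to each subject to review and assess subject compliance, record AEs", along with concomitant medication and reminders. The diary given out at Visit 2 comes back at Visit 3, and 5.11 has staff review it for prohibited medication and adverse events.

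Section 7 foresees the harm: "Severe local skin reactions such as vesiculation/postulation, erosion/ulceration can occur". The synopsis and 8.1.5 compare Test and Reference descriptively on the frequency and distribution of the six reactions. SAP 5.6 says that their severity "will be summarized by treatment group and visit using frequencies and percentages of subjects".

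**The concern.** The six reactions can reach the data by two routes: a grade at a visit, or an adverse event entry when a listed consequence follows. After Visit 2 the first route has a gap of several weeks and the second is narrow. A subject could describe marked ulceration at the Day 15 call, take nothing for it, stay in the study and be healed by Visit 3. Section 5.10, read as written, tells the site not to enter this as an adverse event, and no scheduled grading would pick it up.

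At stake is the safety comparison of Test with Reference. If one product produced more reactions that develop after Day 4 and settle before Day 29, the by-visit tables would not show it. The frequency of reactions in both active arms could also be understated. The primary endpoint, clearance at Day 57, is not affected.

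**Working it through.** The documents state no figure for this gap, so the check is day arithmetic on the visit windows, followed by tracing one case through the recording rules.

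1. **Inputs.** Last planned dose: Day 3 (3.1). Visit 2: Day 4 to 5. Visit 3: Day 29 ± 3, so Day 26 to 32. Visit 4: Day 57 ± 2, so Day 55 to 59. Call: Day 15 ± 3, so Day 12 to 18 (synopsis).

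2. **Ungraded days between Visits 2 and 3** = (day of Visit 3) − (day of Visit 2) − 1.
   - Nominal: 29 − 4 − 1 = 24.
   - Shortest: 26 − 5 − 1 = 20.
   - Longest: 32 − 4 − 1 = 27.

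3. **Position of the call.** Nominally 15 − 4 = 11 days after Visit 2; at the extremes 12 − 5 = 7 and 18 − 4 = 14 days. It falls inside the gap, and the visible description does not include grading.

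4. **Routes to an adverse event after Visit 2.** Three are listed in 5.10.
   - A pause in study medication cannot arise, because the last planned dose is on Day 3.
   - Withdrawal can arise.
   - A new medication can arise, although 4.4 and 5.11 tell subjects to use no other topical product on the treatment area.

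5. **Tracing the case.** Take a reaction that is absent or milder at Visit 2, worsens afterwards, is not treated, does not end participation, and heals before Visit 3.
   - Site-reaction table: no scheduled visit falls in the interval, so there is no required entry.
   - Adverse event record: neither remaining condition in 5.10 is met, so no entry.
   - Day 15 call and diary review: both are described as collecting adverse events, a status that 5.10 withholds.

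6. **Conflict between sections.** Section 7.3 requires every adverse event under the 7.2 definition, including those the participant reports, to be documented, and does not repeat the 5.10 exclusion. Section 7.2 covers any unfavourable sign or symptom. Two sites could therefore treat the same telephone report differently.

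7. **Size.** Let f be the share of severe reactions that are severe only inside the gap and are not otherwise captured. The observed frequency is then the true frequency × (1 − f). The documents give neither term. Purely as illustration, with an assumed true 20%: f = 0 gives 20%, f = 0.25 gives 0.20 × 0.75 = 15%, and f = 0.5 gives 0.20 × 0.5 = 10%. These values show the direction of the effect and are not estimates.

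**The case against.** **The strong reading fails.** A reader might infer that such a reaction is reported nowhere. The documents do not support that. Protocol 5.12.6 allows an unscheduled visit at any time if the investigator thinks it warranted, and the 5.10 rule of grading at each later visit could cover it. Serious events must be reported under 7.4. Pain or infection at the site is an adverse event in its own right. This stands, so the point is confined to there being no *required* place. An unscheduled visit remains discretionary, and under 5.9 subjects are given photographs of these reactions as expected, so it cannot be relied on for capture.

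**Longer reactions are not all missed.** A reader might also infer that a product with longer-lasting reactions would look identical to the other. A reaction that persists to Visit 3 is graded there. Only those healed before that visit escape.

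**Redaction.** The call procedures (5.12.3), the unscheduled-visit list (5.12.6), the schedule of procedures (5.13), parts of 5.10 and the text after the SAP's site-reaction sentence are blacked out. A capture route may be there. This also stands. The exclusion in 5.10 itself is visible.

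**No evidence that anything is lost.** Nothing in the documents shows that f exceeds zero, and the comparison is descriptive only. This lowers the weight of the point. It does not remove the gap, since the design could not show whether f is zero.

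**Separate grading is a legitimate choice.** Keeping expected reactions off the adverse event form is reasonable, provided the separate form covers the period in which they may occur.

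**Conclusion.** The point holds in limited form. The six reactions have three scheduled post-dose gradings (Days 4, 29 and 57), with possible grading at unscheduled visits. Between the first two there are 24 days (range 20 to 27) without scheduled grading. During that time the visible text requires no record of an untreated reaction that arises or worsens after Visit 2, heals before Visit 3, and is mentioned at the call or in the diary.

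How many reactions this affects, and whether it differs between products, cannot be computed from the documents. The conclusion assumes that dosing ends on Day 3 as planned and that the redacted sections contain no further capture rule. It bears on the descriptive safety comparison, not on equivalence or superiority for the primary endpoint.

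**What to change.** In Protocol 5.10, require that any of the six reactions reported at the Day 15 call or in the diary, or seen at an unscheduled visit, be entered on the site-reaction eCRF as a between-visit entry. Record the source (subject-reported or examined) and the onset and end dates. The entry should not by itself make the reaction an adverse event. In SAP 5.6, list or tabulate these entries by treatment group beside the by-visit summary.

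It may be tempting to add a fourth condition to 5.10 that makes severe cases adverse events. That would not be a recording change only. Section 7.4 discontinues a subject who has a severe adverse event related to study drug, so a telephone report could cost the Day 57 assessment and, unless the discontinuation counted as treatment failure, the subject's place in the per-protocol set. The 7.2 definition of severe also leans on the need for treatment, and reactions given a new medication already qualify under 5.10.

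Sections 5.10, 7.3 and 7.4 should be reconciled on how these reactions are classified; this review takes no position on which rule should prevail.

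Cost: a short addition to 5.10, a few eCRF fields, and one listing or table in the SAP. No new visit or assessor is needed, and the entries themselves leave the comparison of any treatment-emergent event unchanged. The limitation is that telephone and diary entries rest on the subject's account rather than a graded examination, so they can be used descriptively only.
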